1.6. Compliance

This study will be conducted in compliance with this protocol, Good Clinical Practice (GCP), and all applicable regulatory requirements.

2. OBJECTIVES

The primary objective of this study is as follows:

- To evaluate the safety and tolerability of dual anti-HIV envelope mAbs, VRC07-523LS and CAP256V2LS, in a sequential regimen with a TLR7 agonist, VES, when administered in virologically suppressed HIV-1 Clade C-infected women on ART and during ATI

The secondary objectives of this study are as follows:

- To evaluate the PK of VRC07-523LS, CAP256V2LS, and VES
- To evaluate whether VRC07-523LS and CAP256V2LS induce anti-VRC07-523LS and/or anti-CAP256V2LS antibodies
- To evaluate the effect of VRC07-523LS and CAP256V2LS in a sequential regimen with VES on viral control or the need for resumption of ART following an ATI.

CCI

3. STUDY DESIGN

3.1. Endpoints

The primary endpoints of this study are as follows:

- The proportion of participants with treatment-emergent AEs
- The proportion of participants with treatment-emergent graded laboratory abnormalities

The secondary endpoints of this study are as follows:

Virology/Efficacy

- Time to viral rebound (confirmed ≥ 50 copies/mL and ≥ 200 copies/mL) following ATI
- The change in plasma viral load set-point following ATI
- Viral load at the end of ATI
- Time to ART resumption following ATI

Pharmacokinetics

- PK parameters for VES in plasma will include Cmax, Tmax, Clast, Tlast, AUCinf, AUClast, AUCexp, t1/2, CL/F, and Vz/F.
- PK parameters for VRC07-523LS and CAP256V2LS in serum will include Cmax, Tmax, Clast, Tlast, AUCinf, AUClast, AUCexp, t1/2, CL, Vss, and Vz.

Immunogenicity

- The proportion of participants with positive anti-VRC07-523LS or anti-CAP256V2LS antibodies

CCI

CCI

3.2. Study Design

This is an open-label, single-center, single-arm study to evaluate a sequential regimen of dual mAbs, VRC07-523LS and CAP256V2LS with a TLR7 agonist, VES, in participants from the Females Rising through Education, Support, and Health (FRESH) cohort.

The FRESH cohort consists of women with HIV-1 Clade C in Durban, South Africa, who were initiated on ART immediately after detection of HIV-1 RNA and are virologically suppressed on ART.

Participants will attend study visits and undergo assessments over 4 periods for a maximum of 60 weeks. During Periods 1 and 2, participants will be evaluated weekly at a minimum and during Periods 3 and 4, every 2 weeks at a minimum. Vesatolimod will be dosed orally, every 2 weeks, for a total of 10 doses during Periods 1 and 2. Participants will receive a first dose of VES alone in Period 1 prior to single, sequential infusions of VRC07-523LS and CAP256V2LS administration 1 week later.

Figure 2. **Study Schema**

Screening ^a	Prebaseline	Period 1 ^b	Period 2 ^c	Period 3 ^d	End-of-Period 3 Visit ^e	Period 4 ^f	ESDD and Follow-Up Procedure ^g	End-of-Study Visit ^h
		Continue ART	ATI from Day 35	ATI		4A-(ART restart ⁱ) or 4B (ATI Extension ^j)		
≤ 35 days	Day -13	Days 0-28	Days 29-133	Days 134-336		Days 337-413		
		VES Doses 1-3 ^k	VES Doses 4-10 ^k	No Dosing		No Dosing		
		VRC07-523LS and CAP256V2LS Doses ^l						

ART = antiretroviral therapy; ATI = analytical treatment interruption; VES = vesatolimod

- a Screening must occur 35 days prior to prebaseline/Day -13 visit.
- b During Period 1, participants will have a study visit every week at a minimum over 4 weeks. Participants will continue to take their ART during this period.
- c During Period 2, participants will have a study visit every week at a minimum over 15 weeks. No VRC07-523LS and CAP256V2LS dose to occur in this period. No ART will be administered and ATI will start from Day 35. If the ART restart criteria are met, the participant may stop Period 2, complete the end-of-Period 3 visit, and restart ART in Period 4A.
- d During Period 3, participants will have a study visit every 2 weeks over 28 weeks. No study drug (VES, VRC07-523LS, or CAP256V2LS) will be administered in this period. No ART will be administered, and ATI will continue. If the ART restart criteria are met, the participant may stop Period 3, complete the end-of-Period 3 visit, and restart ART in Period 4A.
- e The visit will be completed at the end of Period 3 or if ART restart criteria are met prior to starting Period 4A.
- f Participants who have remained virologically suppressed (plasma HIV-1 RNA < 50 copies/mL) or have not met the ART restart criteria by the end of Period 3 will continue into Period 4. The option will be available for either Period 4A, restart of ART for 12 weeks, or Period 4B, to remain off ART for a 12-week ATI extension. The choice of Period 4A or 4B will be at the discretion of the participant and investigator. Participants who meet the ART restart criteria prior to the end of Period 3 may also take part in Period 4A. No study drug (VES, VRC07-523LS, and CAP256V2LS) will be administered in this period.
- g If a participant should discontinue study dosing as described in Section 6.9.1, they will be required to complete an early study drug discontinuation (ESDD) visit and every attempt should be made to keep the participant in the study and continue to perform study procedures. If the participant is unable to complete all scheduled procedures, for criteria other than those described for study discontinuation in Section 3.5., the participant should be followed by telephone for a further duration of time as described in Section 6.9.2. If a participant has completed all study drug dosing but is unable to complete all subsequent visits at the study site, as scheduled in Periods 3 and 4, for criteria other than those described for study discontinuation in Section 3.5. for study discontinuation, the participant they should be followed by telephone for up to 250 days after mAb infusion. During follow up with telephone check-ups, participants should be followed every 4 weeks to monitor for AEs and retrieve urine pregnancy results (kits to be provided at the last study site visit and a positive urine pregnancy result will require confirmation with a serum pregnancy test at the study site). At the end of all follow-up monitoring, participants will undergo the end-of-follow-up visit at the study site.
- i Participants who restart ART in Period 4A will complete 6 study visits scheduled every 2 weeks over a 12-week period.
- j Participants who opt to remain off ART and complete the ATI extension will complete 6 study visits scheduled every 2 weeks over a 12-week period.
- k VES dose administration to occur at baseline/Day 0 and then every 2 weeks up to Dose 10.
- l VRC07-523LS and CAP256V2LS sequential dose administration to occur only once at Day 7.

During Period 1, VRC07-523LS, CAP256V2LS, and VES will be administered together with ART.

Sentinel Dosing: Participants will be enrolled and dosed in a staggered fashion, with a sentinel group consisting of 5 participants conducting Period 1 visits and assessments up to Day 21 first. The safety data of the first 5 participants will be reviewed by an external DMC, and upon confirmation, up to a further 20 participants will be enrolled into Period 1.

During Period 2, the participants will be administered VES and discontinue ART to start ATI with weekly plasma virus monitoring at each study visit.

In Period 3, no treatment (VES, VRC07-523LS, CAP256V2LS, or ART) will be administered, participants will continue ATI and plasma virus levels will be monitored.

At the end of Period 3 or if ART restart criteria are met prior to starting Period 4A, participants will be required to complete an end-of-Period 3 visit.

In Period 4, participants who have remained virologically suppressed (plasma HIV-1 RNA < 50 copies/mL) or have not met the ART restart criteria by the end of Period 3 will continue in either Period 4A and restart ART for 12 weeks, or in Period 4B and remain off ART for a 12-week ATI extension. The choice of Period 4A or 4B will be at the discretion of the participant and investigator.

If the ART restart criteria are met prior to the end of Period 3, participants may also receive ART for 12 weeks in Period 4A.

At the end of Period 4, all participants will complete an end-of-study visit.

If a participant should discontinue study dosing as described in Section [6.9.1](#), they will be required to complete an early study drug discontinuation (ESDD) visit and every attempt should be made to keep the participant in the study and continue to perform study procedures. If the participant is unable to complete all scheduled procedures, for criteria other than those described for study discontinuation in Section [3.5](#), the participant should be followed by as described in Section [6.9.2](#).

If a participant has completed all study drug dosing but is unable to complete all subsequent visits at the study site, as scheduled in Periods 3 and 4, for criteria other than those described for study discontinuation in Section [3.5](#), the participant should be followed by telephone for up to 250 days after mAb infusion.

During follow up with telephone check-ups, participants should be followed every 4 weeks to monitor for AEs and retrieve urine pregnancy results (kits to be provided at the last study site visit and a positive urine pregnancy result will require confirmation with a serum pregnancy test at the study site).

At the end of all follow-up monitoring, participants will undergo the end-of-follow-up visit at the study site..

ART Restart Criteria: Participants will receive ART in Periods 1 and 4A only. In Periods 2, 3, and 4B, participants will be in ATI and will restart ART if they have plasma HIV-1 RNA measurements of \geq 1,000 copies/mL for 8 consecutive weeks and no drop of $0.3 \log_{10}$ from the previous week, or confirmed plasma HIV-1 RNA $>$ 100,000 copies/mL, or a confirmed CD4+ T cell count $<$ 350 cells/ μ L, or if a participant becomes pregnant, or per participant request, or at the discretion of the investigator or sponsor due to other clinical criteria. Once the first confirmed HIV-1 RNA value of \geq 50 copies/mL is detected, this will trigger weekly testing to monitor the HIV-1 RNA measurements.

Known HIV-seronegative male partners to the female study participants may be referred for HIV preexposure prophylaxis (PrEP) to decrease the risk of HIV transmission during ATI.

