To mitigate these risks, plasma viral load and CD4+ T cell count will be measured frequently during ATI, and ART will be promptly reinitiated according to the protocol-defined algorithm. Participants will also be monitored for AEs, and ART will be reinitiated if these are judged (by the investigator and/or sponsor) to be related to the ATI. The initial selection of participants who have a documented detection during acute HIV infection and timing of ART initiation, durable viral suppression for at least 12 consecutive months prior to the screening visit, and the availability of a fully active alternative ART regimen, in the event of discontinuation of the current ART regimen with development of resistance, will further minimize the risks of ATI.

Potential benefits include reduction of the latent HIV-1 viral reservoir, enhanced immune control of virus producing cells, and finally the combination of these effects on HIV-1 viral control (measured as plasma virus rebound and viral load set-point) in the absence of ART. There are no direct benefits to participants participating in this study.

During a pandemic, additional potential risks to the conduct of the study may include adequate study drug availability, interruptions to the study visit schedule, and adherence to protocol-specified treatment regimen, safety monitoring or laboratory assessments. Refer to [Appendix 7](#) for further details on the risks and risk mitigation strategy.

Considering the above, the benefit-risk balance for this study is considered positive.

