3.3. Study Treatments

Participants will receive a single, sequential infusion of VRC07-523LS and CAP256V2LS in combination with a total of 10 VES doses received every 2 weeks during Periods 1 and 2. Participants will receive the first dose of VES alone and VRC07-523LS and CAP256V2LS will be administered 1 week later. Participants will continue their prescribed ART regimen during Period 1, and may restart ART in Period 4A, upon conclusion of Period 3 or if the ART restart criteria are met during Periods 2, 3, and 4B.

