- HIV-specific antibody profiling using plasma (**Days 126 and 133**)
- Whole blood ISG mRNA panel (**Days 56, 57, 126, and 127**)
- Soluble proteins (cytokines, chemokines, and inflammatory markers) (**Days 56, 57, 63, 126, 127, and 133**)
- CD4+ and CD8+ T cell absolute count, percentage, and CD4/CD8 ratio (**Days 42, 56, 70, 84, 98, 112, 126, and 133**)
- PBMC sample for immune cell frequency, activation, and phenotyping (**Days 56, 57, 63, 126, 127, and 133**)
- PBMC sample for HIV-specific T cell responses (**Days 63 and 133**)
- Serum VRC07-523LS PK collection (**Days 56, 84, 112, and 133**)
- Serum CAP256V2LS PK collection (**Days 56, 84, 112, and 133**)
- Plasma dolutegravir PK collection (**Days 56, 84, 112, and 133**)
- Plasma sample for active HIV-1 reservoir (**Days 56, 57, 126, 127, and 128**)
- PBMC sample for active HIV-1 reservoir (**Days 56, 57, 126, 127, and 128**)

- Obtain urine collection for:
 - Urinalysis (**Day 42 and at each visit every 2 weeks thereafter**)
 - Urine pregnancy testing; a positive result will be confirmed with a serum pregnancy test. If the serum pregnancy test is positive, the participant will discontinue from study drug (**Day 42 and at each visit every 4 weeks thereafter**)
- Birth control will be checked and replaced, if required.
- Ongoing eligibility assessment prior to the participant being administered study drug on site (**Days 42, 56, 70, 84, 98, 112, and 126**)
 - Known HIV-1 seronegative sexual partners of enrolled study participants may be referred for HIV PrEP to decrease risk of HIV transmission during ATI.
- Adverse events and changes in concomitant medications will be assessed and recorded. Participants will be reminded to report all symptoms, including flu-like symptoms (eg, fatigue, pyrexia, chills, myalgia, joint pain, or headache) or other unexpected symptoms

6.5. Posttreatment Assessments—Period 3

Participants will have up to 14 study visits every 2 weeks for a total of 29 weeks.

No study drug (VES, VRC07-523LS, or CAP256V2LS) will be administered during this period.

No ART will be administered during this period and ATI will continue. If the ART restart criteria are met, the participant will stop Period 3, complete the end-of-Period 3 visit (Section 6.5.2), and may restart ART in Period 4A.

Upon completion of Period 3, all participants will be required to complete an end-of-Period 3 visit prior to moving into Period 4.

Table 5. Period 3 Study Visits and Study Drug Administration

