6.5.2. End of Period 3 Visit

Participants who complete Period 3 or meet the ART restart criteria will be required to complete an end-of-Period 3 visit 1 week after their last visit (to be completed within \pm 1 day of the protocol-specified visit date [based on the Day 0 visit + the number of postponement days required to confirm ATI eligibility in Period 1, if applicable]). All participants will complete the following procedures:

- Symptom-directed physical examination
- Vital signs (blood pressure, pulse, respiration rate, oxygen saturation, and temperature)

- Body weight
- Review of AEs and changes in concomitant medications
- 12-lead ECG
- Obtain blood samples for:
 - Plasma HIV-1 RNA
 - Plasma HIV-1 resistance testing (in case of viral rebound) to VRC07-523LS, CAP256V2LS, and baseline ART
 - HIV-specific antibody profiling using plasma
 - Whole blood ISG mRNA panel
 - Soluble proteins (cytokines, chemokines, and inflammatory markers)
 - CD4+ and CD8+ T cell absolute count, percentage, and CD4/CD8 ratio
 - PBMC sample for testing of viral sensitivity to the VRC07-523LS and CAP256V2LS mAbs
 - PBMC sample for immune cell frequency, activation, and phenotyping
 - PBMC sample for HIV-specific T cell responses
 - PBMC sample for latent HIV-1 reservoir
 - PBMC sample for active HIV-1 reservoir
 - Plasma sample for active HIV-1 reservoir
- From participants who provide additional consent, lymph node and/or GALT (GALT obtained by rectosigmoid biopsy) tissue collection (within window of \pm 5 days) for some or all of the following tests:
 - Immune cell frequency, activation and phenotype, gene expression and HIV-specific T cell response evaluation (PD and immunology)
 - HIV-1 reservoir measurements (virology)

6.6. Posttreatment Assessments—Period 4

Participants who have remained virologically suppressed (plasma HIV-1 RNA < 50 copies/mL) or have not met the ART restart criteria at the end of Period 3 will continue into Period 4. The option will be available for either Period 4A, restart of ART for 12 weeks, or Period 4B, to remain off ART for a 12-week ATI extension. The period will begin after end of Period 3 Visit

to the end-of-study visit. The choice of Period 4A or 4B will be at the discretion of the participant and investigator.

Participants who meet the ART restart criteria prior to the end of Period 3 may also take part in Period 4A. The first Period 4A visit will require a urine pregnancy test. The ART restart criteria are:

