- b During Period 1, participants will have a study visit every week at a minimum over 4 weeks. Participants will continue to take their ART during this period.
- c During Period 2, participants will have a study visit every week at a minimum over 15 weeks. No VRC07-523LS and CAP256V2LS dose to occur in this period. No ART will be administered and ATI will start from Day 35. If the ART restart criteria are met, the participant may stop Period 2, complete the end-of-Period 3 visit, and restart ART in Period 4A.
- d During Period 3, participants will have a study visit every 2 weeks over 28 weeks. No study drug (VES, VRC07-523LS, or CAP256V2LS) will be administered in this period. No ART will be administered, and ATI will continue. If the ART restart criteria are met, the participant may stop Period 3, complete the end-of-Period 3 visit, and restart ART in Period 4A.
- e The visit will be completed at the end of Period 3 or if ART restart criteria are met prior to starting Period 4A.
- f Participants who have remained virologically suppressed (plasma HIV-1 RNA < 50 copies/mL) or have not met the ART restart criteria by the end of Period 3 will continue into Period 4. The option will be available for either Period 4A, restart of ART for 12 weeks, or Period 4B, to remain off ART for a 12-week ATI extension. The choice of Period 4A or 4B will be at the discretion of the participant and investigator. Participants who meet the ART restart criteria prior to the end of Period 3 may also take part in Period 4A. No study drug (VES, VRC07-523LS, and CAP256V2LS) will be administered in this period.

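### The protocol says both that participants who meet an ART restart criterion will restart ART and that they may, so the main ATI safeguard is not uniformly binding

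*Protocol*

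**What the plan says.** Three places use mandatory wording. The restart paragraph of protocol Section 3.2 says that "participants will be in ATI and will restart ART if they have plasma HIV-1 RNA measurements" at or above the stated level for the stated time, or meet one of the other criteria. The synopsis carries the same paragraph. Section 1.5, in setting out how the risks of ATI are limited, says "ART will be promptly reinitiated according to the protocol-defined algorithm".

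Other places use permissive wording:

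- Schema footnote c, Section 3.2: "If the ART restart criteria are met, the participant may stop Period 2, complete the end-of-Period 3 visit, and restart ART in Period 4A". Footnote d repeats this for Period 3.
- Section 3.2 text, on criteria met before the end of Period 3: "participants may also receive ART for 12 weeks in Period 4A".
- Section 3.3: participants "may restart ART in Period 4A, upon conclusion of Period 3 or if the ART restart criteria are met during Periods 2, 3, and 4B".
- Section 6.4: the end-of-Period 3 visit is to be completed, after which the participant *may* begin Period 4A.
- Section 6.5: "the participant will stop Period 3, complete the end-of-Period 3 visit (Section 6.5.2), and may restart ART in Period 4A".
- Section 6.6: "Participants who meet the ART restart criteria prior to the end of Period 3 may also take part in Period 4A".
- SAP Table 1-1, footnote d: "the participant may stop Period 3, complete the end-of-Period 3 visit, and restart ART in Period 4A". Footnote c matches it for Period 2. The SAP does not reproduce the mandatory paragraph.

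For the analysis, SAP 3.8.1 takes the ART restart date from the recorded start of ART after ATI start. SAP 6.3 measures time to ART resumption from ATI start to that date, censors at the last study date those who do not resume, and flags resumption on or before the end-of-Period 3 visit.

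**The concern.** The restart criteria are the rescue rule for women who stop effective treatment for research purposes, and the risk/benefit section counts prompt restart among the protections. If some sections oblige restart and others permit it, two readers can handle the same viremic participant differently and both claim to follow the protocol.

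The statistical consequence is narrower. Time to ART resumption is a secondary endpoint. If restart follows whenever a criterion is met, much of the Kaplan-Meier curve reflects reaching a virologic or immunologic limit. If restart is optional after that point, the curve also reflects how long people chose to wait. The SAP derives no date on which a criterion was first met, so the two cannot be told apart in the output.

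**Working it through.** **1. Can *may* be read as mere permission to enter Period 4A early?** For some sentences, yes. Sections 6.4 and 6.6 can be taken as opening a period otherwise described for participants who had not met the criteria. Two facts stop that reading from resolving the conflict.

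- Section 6.5 uses both verbs in one sentence: the participant *will* stop Period 3 and *may* restart ART. Stopping is required there and ART is not.
- Section 3.2 confines ART to Periods 1 and 4A. If entry to 4A is optional, so is in-study ART.

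**2. Is stopping the period itself consistent?** No. Footnote d says the participant *may* stop Period 3; Section 6.5 says *will*.

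**3. The plan's own duration.** Section 6.4 starts ATI at Day 35 and Table 5 ends Period 3 at Day 336. (336 − 35)/7 = 43.0 weeks, which reproduces the 43-week maximum ATI in Section 3.4.

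**4. Illustration of the gap.** The documents give no figure for time off ART after a criterion is met. It is (336 − day criterion met)/7, assuming that footnotes c and d are read at their most permissive and that nobody uses the discretionary restart. Section 6.4.1 places the first scheduled ATI sample for HIV-1 RNA at Day 42. The 8-week criterion is at least 1,000 copies/mL for 8 consecutive weeks without a 0.3 log10 drop from the previous week.

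| Scenario | Day met | Weeks to Day 336 |
|---|---|---|
| 8 weeks counted from Day 35 (35 + 56) | 91 | 245/7 = 35.0 |
| 8 weekly values from Day 42 (42 + 49) | 91 | 245/7 = 35.0 |
| 8 weeks from Day 42 (42 + 56) | 98 | 238/7 = 34.0 |
| 8 weeks from Day 56 (56 + 56) | 112 | 224/7 = 32.0 |
| Above 100,000 at Day 42, confirmed Day 49 | 49 | 287/7 = 41.0 |
| Above 100,000 at Day 42, confirmed Day 56 | 56 | 280/7 = 40.0 |

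Postponing ATI under Section 6.3.3 moves both ends of the interval equally and leaves these figures unchanged.

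**5. Effect on the endpoint.** Take ATI start at Day 35 and the Day 98 row, with the SAP formula (event date − ATI start + 1)/7. Restart on the day the criterion is met gives (98 − 35 + 1)/7 = 9.1 weeks. Restart at Day 336 gives (336 − 35 + 1)/7 = 43.1 weeks. The definition is the same in both cases; only the reason for the event differs.

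**The case against.** The strongest reply is that the operative sections do not leave a criterion-meeter in ATI. Section 6.5 stops Period 3. Section 6.4, footnote e and Section 6.5.2 call for the end-of-Period 3 visit once the criteria are met. No section describes such a participant continuing ATI visits to Day 336. Early sustained viremia also looks unlikely: ATI entry requires less than 50 copies/mL (Section 6.3.3), and Section 1.4.3 predicts VRC07-523LS above 20 µg/mL through Week 19. This stands against treating the durations above as expected or as limits. It does not remove the conflict, because under Section 6.5 the period ends but ART is still not required.

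A reader might also infer more than the documents support:

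- *Time to ART resumption has two meanings.* It does not. The SAP fixes one event date, one formula and one censoring rule. Even the mandatory paragraph counts restart at participant request or at investigator or sponsor discretion, so some elective restarts would be present under either wording.
- *Sites could diverge.* The study has a single center.
- *Section 3.3 contradicts Section 3.2 on Period 4B.* Both provide for ART when criteria are met in 4B, and Section 3.2 gives ART only in Periods 1 and 4A. Saying that earlier criterion-meeters may also enter 4A does not close it to others.
- *Section 1.5 contradicts the criteria list on ATI-related adverse events.* Section 1.5 rests on investigator or sponsor judgment, and the list allows restart at their discretion. These are compatible.

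Finally, the endpoint is secondary and descriptive, and SAP 3.5 rules out formal testing. That limits the inferential harm but not the safety relevance.

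**Conclusion.** The point holds as a contradiction about whether restart is obligatory. The synopsis, the Section 3.2 restart paragraph and Section 1.5 cannot be squared with footnotes c and d, the remaining Section 3.2 text, Sections 3.3, 6.4 and 6.5, and the SAP footnotes. Followed as written, the permissive passages leave a stated protection of the ATI non-binding.

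The illustrative size is about 32 to 35 further weeks off ART for the 8-week criterion and about 40 to 41 for confirmed values above 100,000 copies/mL. These are constructed scenarios. A single figure such as 34 weeks should not be quoted as a maximum: it belongs to one starting day, and it needs the footnotes to prevail over Section 6.5. Which instruction is right is not a statistical question and is not judged here.

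**What to change.** The sponsor and investigators should reconcile the passages to one instruction and use it in the synopsis, Section 3.2 and its schema footnotes, Sections 3.3, 6.4, 6.5 and 6.6, and SAP Table 1-1. The same correction should settle whether Period 3 is stopped or may be stopped.

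In SAP 6.3, derive for each participant the date a restart criterion was first met, give the reason for each restart, and list anyone who met a criterion and did not restart. The viral load, CD4 and pregnancy criteria can be derived from scheduled data. The documents do not show whether the eCRF records participant request or discretion as a reason, so those may have to be classified by review.

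The cost is a protocol clarification, one derived date and one listing, for at most 25 participants. SAP 2.3 suggests that end-of-Period 3 visits are already complete, so the analysis change is the more useful part now. SAP Section 1 allows changes after finalization to be documented in the clinical study report.
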